Appendix B: Modified RECIST Incorporating Immune-Related Response Criteria

Conventional response criteria may not be adequate to characterize the antitumor activity of immunotherapeutic agents like MPDL3280A, which can produce delayed responses that may be preceded by initial apparent radiological progression, including the appearance of new lesions. Therefore, modified response criteria have been developed that account for the possible appearance of new lesions and allow radiological progression to be confirmed at a subsequent assessment. In this protocol, patients will be permitted to continue study treatment even after modified Response Evaluation Criteria in Solid Tumors (RECIST) criteria for progressive disease are met if the benefit-risk ratio is judged to be favorable.

These modified criteria are derived from RECIST version 1.1 (v1.1) conventions and immune-related response criteria (irRC).

	RECIST v1.1	Modified RECIST
New lesions after baseline	Define progression.	New measurable lesions are added into the total tumor burden and followed.
Non-target lesions	May contribute to the designation of overall progression	Contribute only in the assessment of a complete response
Radiographic progression	First instance of $\geq 20\%$ increase in the sum of diameters or unequivocal progression in non-target disease	Determined only on the basis of measurable disease; may be confirmed by a consecutive assessment ≥ 4 weeks from the date first documented

Modified RECIST and RECIST, Version 1.1: Summary of Changes

RECIST = Response Evaluation Criteria in Solid Tumors.

Definitions of Measurable/Nonmeasurable Lesions

All measurable and nonmeasurable lesions should be assessed at screening and at the protocolspecified tumor assessment time points. Additional assessments may be performed, as clinically indicated for suspicion of progression.

Measurable Lesions

Tumor Lesions. Tumor lesions must be accurately measured in at least one dimension (longest diameter in the plane of measurement is to be recorded) with a minimum size as follows:

10 mm by CT or MRI scan (CT/MRI scan slice thickness/interval no greater than 5 mm);

10-mm caliper measurement by clinical examination (lesions that cannot be accurately measured with calipers should be recorded as nonmeasurable).

Malignant Lymph Nodes. To be considered pathologically enlarged and measurable, a lymph node must be ≥ 15 mm in the short axis when assessed by CT scan (CT scan slice thickness recommended to be no greater than 5 mm). At baseline and follow up, only the short axis will be measured and followed.

Nonmeasurable Lesions

Nonmeasurable tumor lesions encompass small lesions (longest diameter < 10 mm or pathological lymph nodes with short axis \geq 10 but < 15 mm), as well as truly nonmeasurable lesions. Lesions considered truly nonmeasurable include leptomeningeal disease, ascites, pleural or pericardial effusion, inflammatory breast disease, lymphangitic involvement of skin or lung, peritoneal spread, and abdominal mass/abdominal organomegaly identified by physical examination that is not measurable by reproducible imaging techniques.

Special Considerations Regarding Lesion Measurability

Bone lesions, cystic lesions, and lesions previously treated with local therapy require particular comment, as outlined below.

Bone Lesions

Bone scan, positron emission tomography (PET) scan, or plain films are not considered adequate imaging techniques for measuring bone lesions. However, these techniques can be used to confirm the presence or disappearance of bone lesions.

Lytic bone lesions or mixed lytic-blastic lesions, with identifiable soft tissue components, that can be evaluated by cross-sectional imaging techniques such as CT or MRI can be considered as measurable lesions if the soft tissue component meets the definition of measurability described above.

Blastic bone lesions are nonmeasurable.

Cystic Lesions

Lesions that meet the criteria for radiographically defined simple cysts should not be considered as malignant lesions (neither measurable nor non-measurable) since they are, by definition, simple cysts.

Cystic lesions thought to represent cystic metastases can be considered as measurable lesions, if they meet the definition of measurability described above. However, if noncystic lesions are present in the same patient, these are preferred for selection as target lesions.

Lesions with Prior Local Treatment

Tumor lesions situated in a previously irradiated area or in an area subjected to other locoregional therapy are usually not considered measurable unless there has been demonstrated progression in the lesion. Study protocols should detail the conditions under which such lesions would be considered measurable.

Tumor Response Evaluation

Definitions of Target/Non-target Lesions

Target Lesions

When more than one measurable lesion is present at baseline, all lesions up to a maximum of five lesions total (and a maximum of two lesions per organ) representative of all involved organs should be identified as target lesions and will be recorded and measured at baseline. This means that, for instances in which patients have only one or two organ sites involved, a maximum of two lesions (one site) and four lesions (two sites), respectively, will be recorded. Other lesions (albeit measurable) in those organs will be recorded as non-measurable lesions (even if the size is > 10 mm by CT scan).

Target lesions should be selected on the basis of their size (lesions with the longest diameter) and be representative of all involved organs, but in addition, should lend themselves to reproducible repeated measurements. It may be the case that, on occasion, the largest lesion does not lend itself to reproducible measurement, in which circumstance, the next largest lesion that can be measured reproducibly should be selected.

Lymph nodes merit special mention since they are normal anatomical structures that may be visible by imaging even if not involved by tumor. As noted above, pathological nodes that are defined as measurable and may be identified as target lesions must meet the criterion of a short axis of ≥ 15 mm by CT scan. Only the short axis of these nodes will contribute to the baseline sum. The short axis of the node is the diameter normally used by radiologists to judge if a node is involved by solid tumor. Nodal size is normally reported as two dimensions in the plane in which the image is obtained (for CT, this is almost always the axial plane; for MRI, the plane of acquisition may be axial, sagittal, or coronal). The smaller of these measures is the short axis of 20 mm and qualifies as a malignant, measurable node. In this example, 20 mm should be recorded as the node measurement. All other pathological nodes (those with short axis ≥ 10 mm but < 15 mm) should be considered non-target lesions. Nodes that have a short axis of < 10 mm are considered nonpathological and should not be recorded or followed.

Lesions irradiated within 3 weeks prior to Cycle 1, Day 1 may not be counted as target lesions.

Non-target Lesions

All other lesions (or sites of disease), including pathological lymph nodes, should be identified as non-target lesions and should also be recorded at baseline. Measurements are not required.

It is possible to record multiple non-target lesions involving the same organ as a single item on the Case Report Form (CRF) (eg, "multiple enlarged pelvic lymph nodes" or "multiple liver metastases").

After baseline, changes in non-target lesions will contribute only in the assessment of complete response (ie, a complete response is attained only with the complete disappearance of all tumor lesions, including non-target lesions) and will not be used to assess progressive disease.

Calculation of Sum of the Diameters

A sum of the diameters (longest for non-nodal lesions, short axis for nodal lesions) for all target lesions will be calculated as a measure of tumor burden.

The sum of the diameters is calculated at baseline and at each tumor assessment for the purpose of classification of tumor responses.

Sum of the Diameters at Baseline: The sum of the diameters for all target lesions identified at baseline prior to treatment on Day 1.

Sum of the Diameters at Tumor Assessment: For every on-study tumor assessment collected per protocol or as clinically indicated, the sum of the diameters at tumor assessment will be calculated using tumor imaging scans. All target lesions and all new measurable lesions that have emerged after baseline will contribute to the sum of the diameters at tumor assessment. Hence, each net percentage change in tumor burden per assessment with use of modified RECIST accounts for the size and growth kinetics of both old and new lesions as they appear.

Response Criteria

Evaluation of Target Lesions

Complete Response (CR): Disappearance of all target lesions. Lymph nodes that shrink to < 10 mm short axis are considered normal.

Partial Response (PR): At least a 30% decrease in the sum of the diameters of all target and all new measurable lesions, taking as reference the baseline sum of diameters, in the absence of CR.

Note: The appearance of new measurable lesions is factored into the overall tumor burden but *does not automatically qualify as progressive disease* until the sum of the diameters increases by $\geq 20\%$ when compared with the sum of the diameters at nadir.

Stable Disease (SD): Neither sufficient shrinkage to qualify for PR nor sufficient increase to qualify for PD, taking as reference the smallest sum of the diameters while on study.

Progressive Disease (PD): At least a 20% increase in the sum of diameters of all target and all new measurable lesions, taking as reference the smallest sum on study (this includes the baseline sum if that is the smallest on study). In addition to the relative increase of 20%, the sum must also demonstrate an absolute increase of at least 5 mm.

Impact of New Lesions on Modified RECIST

New lesions alone do not qualify as progressive disease. However, their contribution to total tumor burden is included in the sum of the diameters, which is used to determine the overall modified RECIST tumor response.

Evaluation of Best Overall Response Using modified RECIST

Timepoint Response

It is assumed that at each protocol-specified time point, a response assessment occurs. The following table provides a summary of the overall response status calculation at each time point for patients who have measurable disease at baseline.

Modified RECIST Time point Response Definition

% Change in Sum of the Diameters (Including Measurable New Lesions When Present)	Target Lesion Definition	Non-target Lesion Definition	New Measurable Lesions	New Unmeasurable Lesions	Overall Modified RECIST Timepoint Response
- 100% ^a	CR	CR	No	No	CR
- 100% ^a	CR	Non-CR or not all evaluated	No	No	PR
≤ - 30%	PR	Any	Yes or no	Yes or no	PR
> - 30% to < + 20%	SD	Any	Yes or no	Yes or no	SD
Not all evaluated	Not evaluated	Any	Yes or no	Yes or no	NE
≥+20%	PD	Any	Yes or no	Yes or no	PD

CR, complete response; NE, not evaluable; PD, progressive disease; PR, partial response; RECIST, Response Evaluation Criteria in Solid Tumors; SD, stable disease.

^a When lymph nodes are included as target lesions, the % change in the sum of the diameters may not be 100% even if complete response criteria are met since a normal lymph node is defined as having a short axis of < 10 mm. Any pathological lymph nodes (whether target or non-target) must have reduction in short axis to < 10 mm in order to meet the definition of CR.

Missing Assessments and Inevaluable Designation

When no imaging/measurement is done at all at a particular time point, the patient is not evaluable (NE) at that time point. If only a subset of lesion measurements are made at an assessment, usually the case is also considered NE at that time point, unless a convincing argument can be made that the contribution of the individual missing lesion(s) would not change the assigned time point response. This would be most likely to happen in the case of PD. For example, if a patient had a baseline sum of 50 mm with three measured lesions and at follow up only two lesions were assessed but those gave a sum of 80 mm, the patient will have achieved PD status, regardless of the contribution of the missing lesion

Best Overall Response: All Time Points

The best overall response is determined once all the data for the patient are known. The best overall response according to modified RECIST is interpreted as below:

- **CR**: Complete disappearance of all tumor lesions (target and non-target) and no new measurable or unmeasurable lesions, confirmed by a consecutive assessment ≥ 4 weeks from the date first documented. All lymph nodes short axes must be < 10 mm.
- **PR**: Decrease in the sum of the diameters of all target and all new measurable lesions ≥ 30% relative to baseline, in the absence of CR, confirmed by a consecutive assessment ≥ 4 weeks from the date first documented.
- SD: Criteria for CR, PR, and PD are not met.
- **PD**: Increase in the sum of the diameters of all target and all new measurable lesions ≥ 20% relative to the nadir, which may be confirmed by a consecutive assessment ≥ 4 weeks from the date first documented as follows:

The confirmatory assessment shows an additional measurable increase in tumor burden as measured by the sum of the diameters of all target and all new measurable lesions.

This protocol allows patients to continue to receive study treatment even after confirmed radiographic PD per modified RECIST, and patients may achieve a best overall response of PR or CR based on tumor regression achieved at any time prior to study treatment discontinuation.

Appendix C: Eastern Cooperative Oncology Group Performance Status Scale

ECOG F	ECOG Performance Status								
0	Fully active, able to carry on all pre-disease performance without restriction.								
1	Restricted in physically strenuous activity but ambulatory and able to carry out work of a light or sedentary nature (eg, light house work or office work).								
2	Ambulatory and capable of all self-care but unable to carry out any work activities. Up and about more than 50% of waking hours.								
3	Capable of only limited self-care; confined to bed or chair more than 50% of waking hours.								
4	Completely disabled. Cannot carry on any self-care. Totally confined to bed or chair.								
5	Dead.								

Appendix D: QT Interval on Electrocardiogram Corrected Using the Fridericia's Formula (QTcF)

Fridericia's formula used to correct QT interval for heart rate is:

$$QTcF = \frac{QT}{\sqrt[3]{RR}}$$

where QT_CF is the QT interval corrected for heart rate, RR is the interval from the onset of one QRS complex to the onset of the next QRS complex, measured in seconds, often derived from the heart rate (HR) as 60/HR, and QT is the QT interval measured in milliseconds.

Reference:

Fridericia LS. Die Systolendauer im Elektrokardiogramm bei normalen Menschen und bei Herzkranken. Acta Med Scand 1920; 53: 3469-486.

Appendix E: Pre-Existing Autoimmune Diseases

Patients should be carefully questioned regarding their history of acquired or congenital immune deficiencies or autoimmune disease. Patients with any history of immune deficiencies or autoimmune disease listed in the table below will be excluded from participating in the study. Possible exceptions to this exclusion could be patients with a medical history of such entities as atopic disease or childhood arthralgias where the clinical suspicion of autoimmune disease is low. Patients with a history of autoimmune-related hypothyroidism on a stable dose of thyroid replacement hormone may be eligible for this study. In addition, transient autoimmune manifestations of an acute infectious disease that resolved upon treatment of the infectious agent are not excluded (eg, acute Lyme arthritis). Please contact the Medical Monitor regarding any uncertainty over autoimmune exclusions.

Acute disseminated	Diabetes mellitus Type 1 ^a	Myositis
encephalomyelitis	Dysautonomia	Neuromyotonia
Addison's disease	Epidermolysis bullosa acquista	Opsoclonus myoclonus
Ankylosing spondylitis	Gestational pemphigoid	syndrome
Antiphospholipid antibody	Giant cell arteritis	Optic neuritis
Syndrome	Glomerulonephritis	Ord's thyroiditis
Aplastic anemia	Goodpasture's syndrome	Pemphigus
Autoimmune hemolytic anemia	Graves' disease	Pernicious anemia
Autoimmune hepatitis	Guillain-Barré syndrome	Polyarteritis nodusa
Autoimmune	Hashimoto's disease	Polyarthritis
hypoparathyroidism	IgA nephropathy	Polyglandular autoimmune
Autoimmune hypophysitis	Immune-mediated ocular disease	syndrome
Autoimmune hypothyroidism ^a	(eg, uveitis, episcleritis, iritis)	Primary biliary cirrhosis
Autoimmune myocarditis	Inflammatory bowel disease	Psoriasis
Autoimmune oophoritis	Interstitial cystitis	Reiter's syndrome
Autoimmune orchitis	Kawasaki's disease	Rheumatoid arthritis
Autoimmune thrombocytopenic	Lambert-Eaton myasthenia	Sarcoidosis
purpura	syndrome	Scleroderma
Behcet's disease	Lupus erythematosus	Sjögren's syndrome
Bullous pemphigold	Lyme disease - chronic	Stiff-Person syndrome
Chronic inflammatory	Meniere's syndrome	Takayasu's arteritis
demyelinating	Mooren's ulcer	Ulcerative colitis
polyneuropathy	Morphea	Vasculitis
Chung-Strauss syndrome	Multiple sclerosis	Vogt-Kovanagi-Harada disease
Crohn's disease	Myasthenia gravis	Wegener's granulomatosis
Dermatomyositis	Myasthenia gravis	-

^a Patients with a history of Type 1 diabetes on a stable anti-hyperglycemic regimen or autoimmune-related hypothyroidism on a stable dose of thyroid replacement hormone are eligible for this study.

Appendix F: Anaphylaxis Precautions EQUIPMENT NEEDED

- Tourniquet;
- Oxygen;
- Epinephrine for subcutaneous, IV, and/or endotracheal use in accordance with standard practice;
- Antihistamines;
- Corticosteroids;
- Intravenous infusion solutions, tubing, catheters, and tape.

PROCEDURES

In the event of a suspected severe or life-threatening anaphylactic reaction during study drug infusion, the following procedures should be performed:

- 1. Stop the study drug infusion.
- 2. Apply a tourniquet proximal to the injection site to slow systemic absorption of study drug. Do not obstruct arterial flow in the limb.
- 3. Maintain an adequate airway.
- 4. Administer antihistamines, epinephrine, or other medications as required by patient status and directed by the physician in charge.
- 5. Continue to observe the patient and document observations.

Appendix G: New York Heart Association Classification of Functional Cardiac Capacity

Class	Description						
Ι	No limitation: Ordinary physical activity does not cause undue fatigue, dyspnea, or palpitation.						
II	Slight limitation of physical activity: Such patients are comfortable at rest. Ordinary physical activity results in fatigue, palpitations, dyspnea, or angina.						
III	Marked limitation of physical activity: Although patients are comfortable at rest, less than ordinary physical activity will lead to symptoms.						
IV	Inability to carry on physical activity without discomfort: Symptoms of congestive heart failure are present even at rest. With any physical activity, increased discomfort is experienced.						

From: Criteria Committee, New York Heart Association, Inc. Diseases of the heart and blood vessels. Nomenclature and criteria for diagnosis. 6th ed. Boston, Little, Brown and Co, 1964:114.

Appendix H: The Modified Toxicity Probability Interval (mTPI) Method

The modified toxicity probability interval methodology is described in detail in Ji et al, 2010, and Ji et al, 2013. A short summary is given below.

Dose-finding method:

The mTPI design employs a simple beta-binomial hierarchical model. Decision rules are based on calculating the probability of three outcomes corresponding to underdosing, proper dosing, and overdosing in terms of toxicity.

Consider d dose levels of a certain cytotoxic drug in a phase 1 trial. Let pi be the unknown probability of toxicity associated with the i-th dose, $I = 1, \ldots, d$. The toxicity probability usually increases with the dose level, so we assume $p_1 < p_2 < \ldots < p_d$. Suppose that dose i is currently used for treating patients and n_i ($n_i \ge 1$) patients have been treated at this dose. Suppose x_i ($x_i \le n_i$) patients experienced toxicity. Based on the observed values of x_i and n_i , we assume that physicians choose one of the following three decisions:

- 1. de-escalate (D) to the next lower dose (i-1);
- 2. stay (S) at the same dose i; or
- 3. escalate (E) to the next higher dose (i+1).

Depending on the decision, the next cohort is treated at dose j which can be one of the 3 doses $\{i-1, i, i+1\}$; the values of x_j and n_j are then observed for the new cohort, and an appropriate decision is chosen once again. The trial thus proceeds with the next cohort.

These additional rules are important for practical concerns:

- Safety rule 1 (early termination): Suppose that dose 1 has been used to treat patients. If there is greater than a 95% probability that toxicity with dose 1 is greater than the target toxicity level (33%), then terminate the trial due to excessive toxicity.
- Safety rule 2 (dose exclusion): Suppose that the decision is E, to escalate from dose i to (i+1). If there is greater than 95% probability that toxicity with dose i+1 is greater than the target toxicity level (33%), then treat the next cohort of patients at dose i and exclude doses (i+1) and higher from the trial, that is, these doses will never be used again in the trial.
- At the end of the trial, select as the MTD, the dose with the estimated probability of toxicity closest to 33%.

Implementation of the mTPI in Study CO-1686-018:

The decision table for escalating, reducing or maintaining the same dose is based on algorithm provided by Ji et al, 2010, with the following 3 inputs:

- 1. Maximum of 14 patients treated at any dose
- 2. Target toxicity probability of 33%
- 3. Equivalence interval of 5% so that any dose with an estimated probability of toxicity in the interval [28%, 38%] can be selected as the MTD

References:

Ji Y and Wang S-J. Modified Toxicity Probability Interval Design: A Safer and More Reliable Method Than the 3+3 Design for Practical Phase 1 Trials. J Clin Oncol 2013;31:1785-91.

Cohort Decision Table

Number of patients treated at current dose

	1	2	3	4	5	6	7	8	9	10	11	12	13	14
0	Е	Е	Е	E	Е	Е	Е	Е	Е	E	E	Е	Е	Е
1	D	S	S	S	S	Е	Е	Е	Е	Е	Е	Е	Е	E
2		DU	D	S	S	S	S	S	S	Е	Е	Е	Е	E
3			DU	DU	D	S	S	S	S	S	S	S	S	S
4				DU	DU	DU	D	S	S	S	S	S	S	S
5					DU	DU	DU	DU	D	S	S	S	S	S
6						DU	DU	DU	DU	DU	D	S	S	S
7							DU	DU	DU	DU	DU	DU	D	S
8								DU						
9									DU	DU	DU	DU	DU	DU
10										DU	DU	DU	DU	DU
11											DU	DU	DU	DU
12												DU	DU	DU
13													DU	DU
14														DU
	г										7			

E = Escalate to the next higher dose S = Stay at the current dose D = De-escalate to the next lower dose U = The current dose is unacceptably toxic MTD=33% Sample size = 14

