3.1 Clinical Safety Committee

Throughout the study, oversight will be provided by the Clinical Safety Committee (CSC), comprised of all Principal Investigators, the Sponsor's Medical Monitor and the Sponsor's drug safety representative. The CSC will:

- Review and confirm all DLTs;
- Determine all cohort dose-escalation and de-escalation decisions (assignment of Dosing Cohorts) during the Dose Finding Phase (Phase 1);
- Determine the MAD or MTD and RP2D to extend into the Expansion Phase (Phase 2), based on available safety, tolerability, and PK data;
- Review safety data for all patients during Phase 1 and Phase 2.

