3.2.2 Assignment of Dosing Cohorts

Specific doses of rociletinib will be administered in combination with a fixed dose of MPDL3280A. Combination doses of rociletinib with MPDL3280A will be defined for each Dosing Cohort enrolled during the Dose Finding Phase, and currently two potential Dosing Cohorts are planned (see Table 5). The first Dosing Cohort will be 500 mg BID rociletinib and 1200 mg MPDL3280A on Day 1 of each 21-day cycle. At minimum, 3 patients will be enrolled into this cohort. If this combination dose is determined to be safe and tolerable, no further dose modifications for either drug will be made. Based on emerging safety and evaluable PK and/or pharmacodynamics data, the CSC may evaluate additional doses or schedules of rociletinib.

Cohort	Rociletinib Dose	MPDL3280A Dose
1	500 mg PO BID	1200 mg IV every 3 weeks
-1	375 mg PO BID	Day 1 of each 21-day cycle

Table 5:Phase 1 Dosing Cohorts

BID, twice daily; IV, intravenous; PO, oral.

A modified toxicity probability interval (mTPI) method (Appendix H) will be used to guide decisions on assignment of patients to different Dosing Cohorts. Compared with the 3+3 design, the mTPI method reduces the risk of exposing patients to doses above the MTD, which is defined as the acceptable daily oral dose with estimated probability of toxicity closest to 33%. The mTPI design is a model-based approach that has a pre-specified decision matrix that recommends escalating, reducing or maintaining the same dose or stopping dose escalation, based on the number of DLTs observed in the dose level under evaluation. Consequently, patients enrolled into the trial can be allocated to appropriate doses without conducting additional computations.

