At each dose level, after the first evaluable 3 patients have completed Cycle 1, the CSC will meet to evaluate the Dosing Cohort data and to make a decision on the next step for Dosing Cohort assignment (increase dose, decrease dose, maintain same dose, or stop), which will be guided by the mTPI decision table (Appendix H). A patient will be deemed evaluable for safety and DLT determination if they have received at least 75% of the planned total dose of each drug within Cycle 1. Patients who receive <75% of the planned total dose of either rociletinib or MPDL3280A for reasons other than study drug-related AEs will not be included in the evaluation of the Dosing Cohort and will be replaced. If the dose is maintained, up to an additional 6 patients may be enrolled at the same dose, and the next safety evaluation will take place after all patients have completed Cycle 1. The CSC may decide to meet at any time to evaluate a Dosing Cohort if a safety signal arises or other data become available to justify re-evaluation of the Dosing Cohort before it is fully enrolled.

The enrollment/evaluation process will continue until at least 6 patients have been treated at any single dose level or enrollment of the maximum sample size of 18 patients for the Phase 1 portion of this study has been achieved.

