3.2.3 Recommended Phase 2 Dose

The RP2D will be determined by the CSC based on cumulative data from all Dosing Cohorts in the Dose Finding Phase. A Safety Expansion Cohort of up to 6 patients may be enrolled to further examine the tolerability of a dose combination of interest or the tolerability of the combination dosing without a rociletinib Run-in-Period.

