10.2.5 Safety Analyses

The safety analyses will be performed using the safety population.

Safety data analysis will be conducted on all patients receiving at least one dose of rociletinib or MPDL3280A. The number and percentage of patients experiencing one or more AEs will be summarized by dose level group, relationship to study drug, and severity. AEs will be coded using MedDRA terminology. Listings of patients who experienced DLT during Cycle 1, dose reductions, dosing interruptions, withdrawal due to an AE, SAEs and/or death will be presented. Laboratory parameters will be summarized using descriptive statistics, by post-dosing shifts relative to baseline, and data listings of clinically significant abnormalities. Vital signs, ECOG performance status, and ECG data will be summarized by changes from baseline values at each dose level using descriptive statistics.

A mTPI method will be used to identify the MTD or MAD and the RP2D. The mTPI, a model-based approach that has a pre-specified decision matrix that recommends escalating, reducing or maintaining the same dose or stopping dose escalation, based on the toxicities observed in the dose level under evaluation, reduces the risk of exposing patients to doses above the MTD compared with 3+3 design in which there is a 71% chance of escalation if the true but unknown rate of DLT is 20% and less than 50% chance of escalation if the true but unknown rate of DLT is higher than 30%.

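### Appendix H's end-of-trial rule can name 500 mg BID as the MTD at an observed DLT rate of 50%, and no written limit prevents it

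*Combined protocol and SAP*

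**What the plan says.** Section 3.2.2 and Table 5 plan two rociletinib doses with fixed-dose MPDL3280A: 500 mg BID first, and 375 mg BID as cohort -1. Nothing higher is listed, although the CSC may add doses or schedules. At least 3 patients enter the first cohort. After that, "If the dose is maintained, up to an additional 6 patients may be enrolled at the same dose". On stopping: "The enrollment/evaluation process will continue until at least 6 patients have been treated at any single dose level", or until the Phase 1 maximum of 18 is reached.

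The Appendix H table prints S at 3/6 and 4/9, DU at 4/6 and D at 5/9. For the final choice the appendix says: "At the end of the trial, select as the MTD, the dose with the estimated probability of toxicity closest to 33" percent. Input 3 to the table says that "any dose with an estimated probability of toxicity in the interval [28%, 38%] can be selected as the MTD".

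Section 3.2.2 adds that the MTD must be *acceptable*, and that 500 mg stands if judged safe and tolerable. Neither condition carries a number. Section 3.1 gives the CSC this task: "Determine the MAD or MTD and RP2D to extend into the Expansion Phase (Phase 2), based on available safety, tolerability, and PK data". Section 3.2.3 offers an option: "A Safety Expansion Cohort of up to 6 patients may be enrolled to further examine the tolerability". Outside Appendix H, the only numerical DLT limit on a dose in this study is in Section 5.7.4: a rate below 33% before an individual Phase 1 patient may move up to that dose.

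The mTPI is justified in Section 3.2.2 with "Compared with the 3+3 design, the mTPI method reduces the risk of exposing patients to doses above the MTD". Section 10.2.5 gives the comparator as a "3+3 design in which there is a 71% chance of escalation if the true but unknown rate of DLT is 20" percent.

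**The concern.** When the trial starts at its top planned dose, escalating too far is not the issue. What matters is whether the rules let go of 500 mg when they should. A rule that picks the dose closest to 33% protects patients only if there is another dose to compare with, or a ceiling. On the shortest permitted path there is neither: 500 mg has 6 patients, 375 mg has none, and the rule must return 500 mg whatever its distance from 33%, unless a DU or D code has already intervened.

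The RP2D goes to up to 75 Phase 2 patients, who start both drugs on C1D1 without a run-in (Section 3.3).

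**Working it through.** **1. Reproduce the table.** Inputs from Appendix H: target 33%, interval 28% to 38%, and U when the probability that toxicity exceeds 33% is above 95%. A Beta(1,1) prior is assumed, as none is stated. For x DLTs in n patients the posterior is Beta(1+x, 1+n-x). The code is the interval (under, stay, over) with the largest posterior mass divided by width. All 91 cells in the rows for 0 to 7 DLTs match the print.

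| DLTs/n | Observed | Posterior mean (x+1)/(n+2) | Mass/width: under, stay, over | P(p>33%) | Code |
|---|---|---|---|---|---|
| 3/6 | 50.0% | 50.0% | 0.36, 1.51, 1.21 | 83.2% | S |
| 4/9 | 44.4% | 45.5% | 0.42, 2.00, 1.10 | 79.4% | S |
| 4/6 | 66.7% | 62.5% | 0.08, 0.57, 1.49 | 95.7% | DU |
| 5/9 | 55.6% | 54.5% | 0.12, 1.01, 1.40 | 92.7% | D |

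So 3/6 and 4/9 exceed 38% on either estimate, and neither reaches the 95% safety cut.

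**2. How often a first pass ends there.** A first pass is the run at 500 mg before any move to 375 mg. E at 500 mg is read as maintain. The first 3 patients must have 0 or 1 DLT (2/3 is D, 3/3 is DU); then 3 or 6 more are added. With binomial probabilities at true rate p:

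- End at 3/6 = P(0/3)P(3/3) + P(1/3)P(2/3). At p = 0.50: 0.125×0.125 + 0.375×0.375 = 0.156.
- End at 4/9 = P(0/3)P(4/6) + P(1/3)P(3/6). At p = 0.50: 0.125×0.234 + 0.375×0.3125 = 0.146.
- 500 mg kept at 6, S counted as kept = P(0/3) + P(1/3)(1-p³). At p = 0.50: 0.125 + 0.375×0.875 = 0.453. With 3/6 barred: 0.453 - 0.156 = 0.297.

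| True DLT rate (assumed) | 25% | 33% | 40% | 50% |
|---|---|---|---|---|
| Ends at 3/6 | 7% | 11% | 14% | 16% |
| Ends at 4/9 (3+6 path) | 7% | 12% | 15% | 15% |
| Kept at 6, S counted as kept | 84% | 73% | 62% | 45% |
| Kept at 6, 3/6 barred | 77% | 62% | 48% | 30% |
| Kept at 9, S counted as kept | 83% | 70% | 56% | 36% |
| Kept at 9, 4/9 barred | 76% | 58% | 41% | 21% |

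**3. The estimator.** Once both doses have data, the unnamed estimator can change the answer. Take 2/3 at 500 mg (D), 0/3 at 375 mg (E), then 1 DLT in 3 more at 500 mg, giving 3/6. The return is not blocked, since P(p>33%) at 2/3 is 89%. Distances from 33%:

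- Raw proportions: |50-33| = 17 points for 500 mg and |0-33| = 33 for 375 mg, so 500 mg is named.
- Posterior means: |50-33| = 17 for 500 mg and |20-33| = 13 for 375 mg, so 375 mg is named.

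**4. The 3+3 comparison.** The 3+3 escalation chance is (1-p)³ + 3p(1-p)²(1-p)³. It gives 70.9% at p = 0.20 and 49.4% at p = 0.30, matching Section 10.2.5. Expected first-pass patients at 500 mg at p = 0.50:

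- Table, stopping at 6: 3 + 3(0.125 + 0.375) = 4.5.
- 3+3: 3 + 3×0.375 = 4.1, or 4.5 if it also fills 6 before keeping the dose.

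The table's exposure is not lower.

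**The case against.** A reader might infer that Appendix H contains two opposed selection rules, one of which forbids any dose above 38%. The text does not support that. Input 3 is listed as an input to the decision table, and its wording permits selection within the interval without forbidding it elsewhere. Read as exclusive, it would also bar 0/6 and 1/6. The explicit end-of-trial rule is the closest-to-33% one. This narrows the point to a rule with no ceiling that can name a dose outside the appendix's own interval.

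The words *acceptable* and *safe and tolerable* do act as gates, and the RP2D is a CSC decision. S also means stay: Section 3.2.2 allows more patients, and the optional safety cohort may test dosing without a run-in. All this stands. But the gates have no number, more patients are allowed and not required, and ending at 3/6 complies with the text.

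Appendix H calls itself a summary of cited papers, which may name an estimator; the protocol does not.

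A reader might also infer that mTPI is much less safe here than 3+3, because a 3+3 design keeps 500 mg in 60%, 43%, 31% and 17% at the four assumed rates. That is not a like-for-like comparison: the gap in retention is largely due to the 33% target, and the exposure difference at a true 50% is 0 to 0.4 patients. Only the claimed reduction is unsupported.

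**Conclusion.** The point holds as a gap in the final selection rule; the decision table itself is correct. A complying trial can end at 3/6 or 4/9 on 500 mg with 375 mg untested, and the written rule then names 500 mg as the MTD. No numerical limit stops that dose from becoming the RP2D.

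The size depends on true combination DLT rates that the documents do not give. Monotherapy rates were below 33% at every dose (Section 1.3.1) and MPDL3280A had no DLTs (Section 1.4.1), so 50% is a stress case. Across 25% to 50%, 7% to 16% of first passes end at 3/6 and 7% to 15% at 4/9 on the 3+6 path. These figures describe the written guidance. A reader might take the retention figures as the chance that the CSC selects 500 mg, but the CSC also weighs tolerability and PK and may decline the dose.

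**What to change.** In Section 3.2.2 and Appendix H:

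- State that a dose with an observed DLT rate above 38% cannot be the MTD or RP2D, and that this overrides an S in the table when dose finding would otherwise end. Observed rates and posterior means give the same decision at 2/6 (33%, 37.5%), 3/6 (50%, 50%), 3/9 (33%, 36%) and 4/9 (44%, 45%).
- At 3/6 on 500 mg, do not stop. Add 3 patients, keep 500 mg only at 3/9, and otherwise open 375 mg. If 6 are added in one step after the first 3, keep it at 3/9 or fewer.
- State that the 28% lower bound does not bar any tested dose; a dose below it may be the MAD or RP2D.
- Apply the same ceiling at 375 mg. On D, DU or a final rate above 38% there, no planned dose is acceptable, and the CSC stops combination dosing or amends the protocol.
- Name the estimator for closest to 33%, for example the posterior mean.
- Qualify the 3+3 comparison here and in Section 10.2.5.
- Clerical: the implementation heading names CO-1686-018 and should name CO-1686-032. Map dose 1 to 375 mg and dose 2 to 500 mg, so that the early-termination rule refers to the right dose.

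**Cost.** Short text edits, and up to 3 more patients at 500 mg in 7% to 16% of first passes. Retention becomes (kept with 3/6 barred) + P(end at 3/6)×P(0/3). At a true 25% this is 0.771 + 0.066×0.422 = 0.799, so 80% against 84% now; at 33%, 40% and 50% it is 65%, 51% and 32%, against 73%, 62% and 45%. With 9 patients at 500 mg and 6 at 375 mg, 15 of the 18 are used. If 375 mg also went to 9, all 18 would be used, leaving none for replacements. The plan should also say whether the optional safety cohort counts within the 18.
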